4. TRIAL DESIGN

4.1. Primary and secondary parameters to be determined during the study

Primary variable:

- Change in HFcomponent after 5-minute exposure to the VR audio-visual sequence;

Secondary variables:

- rMSSD variable after 5-minute exposure to the VR audio-visual sequence;

- LF/HF ratio after 5-minute exposure to the VR audio-visual sequence;
- SDNN variable after 5-minute exposure to the VR audio-visual sequence;
- Total power (TP) variable after 5-minute exposure to the VR audio-visual sequence;
- HR variable after 5-minute exposure to the VR audio-visual sequence;
- BP variable after 5-minute exposure to the VR audio-visual sequence;
- Spielberger State-Trait Anxiety Inventory (STAI) variable after 5-minute exposure to the VR audio-visual sequence.

The criterion for the prevailing efficiency for each variable is the presence of statistically significant differences between groups in favour of any of the groups with a directivity, which indicates the effectiveness of the impact of the studied VR technology.

Tolerability evaluation

Tolerability of the VR technology will be evaluated based on: vital signs, assessment of AR/ADE.

Upon completion of the study (upon completion of Visit 2), the Investigator should provide an assessment of the tolerability of the studied VR technology for each healthy volunteer based on the 5-point verbal analogue scale given in Table 1.

Table 1. Tolerability evaluation

Points	Category	Category description
5 points	“very good ”	No adverse reactions associated with the VR technology
4 points	“good”	There is a minor adverse effect that does not cause serious problems in a healthy volunteer and does not require discontinuation of the use of the VR technology.
3 points	“satisfactory”	There is a minor adverse effect that causes discomfort in a healthy volunteer, but does not require discontinuation of the use of the VR technology.
2 points	“unsatisfactory”	There is an adverse reaction that causes a significant negative effect on the condition of a healthy volunteer, it requires discontinuation of the use of the VR technology, but does not require additional medical care
1 point	“extremely unsatisfactory”	There is an adverse reaction that causes a significant negative effect on the condition of a healthy volunteer, it requires discontinuation of the use of the VR technology and additional medical care

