7. EFFICACY EVALUATION

7.1. Efficacy parameters

Principal and secondary parameters to be determined during the study:

Primary variable:

- Change in HF component after 5-minute exposure to the VR audio-visual sequence;

Secondary variables:

- Change in rMSSD after 5-minute exposure to the VR audio-visual sequence;
- Change in LF/HF ratio after 5-minute exposure to the VR audio-visual sequence;
- Change in SDNN after 5-minute exposure to the VR audio-visual sequence;
- Change in TP after 5-minute exposure to the VR audio-visual sequence;
- Change in HR after 5-minute exposure to the VR audio-visual sequence;
- Change in BP after 5-minute exposure to the VR audio-visual sequence;
- Change in Spielberger State-Trait Anxiety Inventory (STAI) score after 5-minute exposure to the VR audio-visual sequence.

The criterion for the prevailing efficiency for each variable is the presence of statistically significant differences between groups in favour of any of the groups with a directivity, which indicates the effectiveness of the technology. Procedures and methods required for efficacy evaluation are described in Section 4.13. The time and events schedule is shown in Section 4.12.

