9. STATISTICS

9.1 Justification of the sample size

The required sample size is the minimum sufficient number of subjects to obtain clinically and statistically significant outcomes of the clinical trial. Depending on the type of clinical trial and its design, as well as the types of variables used to evaluate the treatment effect, the sample size may vary.

The sample size depends on the following parameters:

- The size of the clinically significant differences (δ);
- Limiting probability of type I error α (usually for the tests of the prevailing efficiency is equal to 0.05 or 5% (two-tail));
- Limiting probability of type II error β (usually equal to 0.2) and, respectively, the power (80 %);
- Estimated on the basis of previous studies of intrasubject variability.

This study is designed to prove the superiority of the use of VR headset A vs. the use of the VR headset B for the main variable — “Change in HFcomponent after 5-minute exposure to the audio and visual VR sequence”.

To estimate the sample size, it is assumed that the following statistical hypotheses are verified for the demonstration of superiority under conditions of the single-group design:

$$H_0: \varepsilon \leq \delta \text{ vs. } H_a: \varepsilon > \delta, \quad (1)$$

where δ — the limit of superiority — the marginal value of the clinically significant differences in which it can be assumed that the investigational device (VR headset A) is superior to the comparable device (VR headset B);

$$\varepsilon = \mu_A - \mu_B \quad (2)$$

true difference between the arithmetic mean of the results obtained using the VR headset A and the VR headset B.

According to Chow et al [18], the sample size can be estimated using the following expression:

$$n = \frac{(z_{\alpha} + z_{\beta})^2 \sigma_m^2}{2(\varepsilon - \delta)^2} \quad (3)$$

where d — the size of clinically important differences as determined by experts; a — limiting probability of type I error (significance level), which in most cases is equal to 0.05 (5%); b — limiting probability of type II error; s_m — coefficient of variation, which is evaluated based on the results of previous studies.

In this study, the size of the clinically important differences d is 0.1 (10%), $a = 0.05$ (two-tailed), $b = 0.05$ (study power of 95 %). It is assumed that the difference e will be 0.25 (25 %), and s_m will be 0.35 (35 %). The results of calculations are given in the table below:

Statistical parameter	Value

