9.2.3 Efficacy analysis

Efficacy analysis based on quantitative variables

For each quantitative parameter, estimate its relative change after the exposure of the headset in comparison with the values before its exposure in % compared with the baseline using the following formula:

$$X(\%) = \frac{T_{\text{нiсiя}} - T_{\text{до}}}{T_{\text{до}}} \times 100\% \quad (3).$$

Give descriptive statistics values (n, arithmetic mean, median, standard deviation, minimum and maximum value) for each time point, grouping the data separately for each headset, and, also, show the difference between these indicators for each headset (“after” – “before”), and between the headsets (“VR headset A” – “VR headset B”). Present changes of the parameters over time graphically.

To analyse the efficacy of the four-factor dispersion analysis (ANOVA) based on the mixed model: the “exposure sequence” factors (levels “A – B” and “B – A”, “exposure period” (levels: “Period 1” and “Period 2” and “headset” (levels: “VR headset A” and “VR headset B”) are fixed, the “subjects” factor is random, distributed in the “exposure sequence” factor followed by the use of contrast analysis between the levels of the “headset” factor (level “VR headset B” – reference).

Check the normal distribution of the ANOVA residues using the Shapiro-Wilk test. In case the residues are not distributed normally, perform the ANOVA on ranks [19].

Efficacy analysis based on categorical variables

Calculate the descriptive statistics parameters (frequency and proportion in percentage).

Present results graphically.

To compare the proportions for the “VR headset A” and the “VR headset B” McNemar’s test should be used. In case the categorical variable has more than two categories, the marginal frequency test should be used.

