9.2.5 Significance levels

The level of significance is equal to 0.01 for the Shapiro-Wilk test, and equal to 0.05 for other tests.

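### Section 9.1 defines superiority as A beating B by more than a 10% limit, but the success criterion and planned analysis test only for a difference from zero, and the rank fallback as written cannot address the limit

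*Protocol*

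**What the plan says.** Section 9.1 says the trial is meant to prove that headset A is superior to headset B on the change in HF. It writes H0: ε ≤ δ against Ha: ε > δ and describes δ as "the marginal value of the clinically significant differences in which it can be assumed that the investigational device (VR headset A) is superior" to the comparator. The parameter ε is the "true difference between the arithmetic mean of the results obtained using the VR headset A and the VR headset B". The section then says that "the size of the clinically important differences d is 0.1 (10"%), assumes ε = 0.25 and s_m = 0.35, takes α = 0.05 two-tailed and 95% power, and arrives at 36 volunteers. About 100 are to be randomised.

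The sections that decide success do not use the limit:

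- Section 4.1: "The criterion for the prevailing efficiency for each variable is the presence of statistically significant differences between groups", in the direction that indicates effectiveness.
- Section 7.1 repeats this: "the presence of statistically significant differences between groups in favour of any of the groups".
- Section 9.2.3 fits a mixed-model ANOVA "followed by the use of contrast analysis between the levels of the" headset factor, with headset B as reference.
- Section 9.2.3 also gives the fallback: "In case the residues are not distributed normally, perform the ANOVA on ranks".
- Section 9.2.5: "The level of significance is equal to 0.01 for the Shapiro-Wilk test, and equal to 0.05 for other tests".

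**The concern.** The protocol holds two definitions of superiority. Under 9.1, A must beat B by more than 10%. Under 4.1, 7.1 and 9.2.3, A need only differ from B significantly in the right direction. An ordinary contrast against a reference level tests A − B = 0. Nothing in 9.2.3 shifts that null or compares a confidence bound with 0.10, and the only instruction on 95% confidence intervals (9.2.2) concerns the baseline description.

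The rank fallback widens the gap. A contrast of ranks does not estimate a difference in arithmetic means, which is how 9.1 defines ε, so as specified the limit has no counterpart on that route.

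The primary claim is at stake. A significant contrast could be reported as the superiority defined in 9.1 when only a non-zero difference was tested.

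**Working it through.** **Inputs.** From 9.1: z_α = 1.96, z_β = 1.64, ε = 0.25, δ = 0.10, s_m = 0.35. Number randomised: 100 (9.1; also 4.3).

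**Step 1: reproduce the protocol's figure.** Formula (3) is n = (z_α + z_β)² s_m² / [2(ε − δ)²].

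- δ = 0.10: (3.60)² × 0.35² / (2 × 0.15²) = 1.5876 / 0.045 = 35.28, rounded up to **36**, as stated.
- δ = 0: 1.5876 / (2 × 0.25²) = 1.5876 / 0.125 = 12.70, rounded up to **13**.

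The stated 36 therefore depends on the limit.

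**Step 2: standard error of A − B with 100 completers.** The protocol does not make clear what 0.35 measures, or whether formula (3) gives a total or a number per sequence, so three readings are carried:

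- (i) SD of the A − B difference: 0.35/√100 = 0.0350. Formula (3) with 50 per sequence gives the same value.
- (ii) Intrasubject SD of a single reading: 0.35 × √2/√100 = 0.0495.
- (iii) Formula (3) with n = 100 in total: 0.35/√200 = 0.0247.

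**Step 3: compare the two decision rules.**

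| Quantity | Formula | (i) | (ii) | (iii) |
|---|---|---|---|---|
| Smallest observed A − B passing the zero test | 1.96 × SE | 0.069 | 0.097 | 0.049 |
| Smallest observed A − B passing a test of the limit | 0.10 + 1.96 × SE | 0.169 | 0.197 | 0.149 |
| P(zero test favours A), true ε = 0.10 | Φ(0.10/SE − 1.96) | 0.815 | 0.524 | 0.981 |
| P(zero test favours A), true ε = 0.05 | Φ(0.05/SE − 1.96) | 0.298 | 0.171 | 0.524 |
| Power of the limit rule, true ε = 0.25 | Φ(0.15/SE − 1.96) | 0.990 | 0.858 | >0.999 |

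For reading (i) at ε = 0.10: 0.10/0.035 − 1.96 = 0.897, and Φ(0.897) = 0.815. A t reference with 98 degrees of freedom changes these probabilities by less than 0.01.

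**Step 4: does the result need 100 volunteers?** With 36 in place of 100, the zero-test thresholds are 0.114, 0.162 and 0.081, and the probability of success at a true 0.10 is 0.40, 0.23 and 0.68. The thresholds move, but the error rate against the null of 9.1 stays far above 2.5%. Since Φ(0.10/SE − 1.96) exceeds 0.025 for any finite SE, the direction does not depend on the reading or on the sample size.

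**The case against.** The best counter-argument is that δ was only a sizing device. Section 9.1 introduces its hypotheses for the purpose of estimating the sample size and under a single-group design, which this cross-over trial is not. On that reading the trial is sized on a harder hypothesis than it tests, which only adds power. Against a zero null there is no inflation, and the 52% to 98% is simply power to detect a real effect of 0.10. This reading is possible. It does not make the text consistent: 9.1 also says what the trial is designed to prove and defines superiority by δ. If δ is for sizing only, the hypothesis and the 36 do not match the planned test.

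Other points stand in part:

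- The sizes depend on the reading of 0.35 and on 100 completers. Withdrawals are not replaced. Under reading (ii) with a t reference, 96 completers would put the zero-test threshold at 0.1003, just above the limit. The error rate at a true 0.10 would still be far above 2.5%.
- Ranks could be made to carry the limit by subtracting 10 points from the headset A values before ranking. The protocol specifies no such step, and the result would still not estimate a mean difference.
- Section 9.2.3 asks for descriptive statistics of A − B, so a reader could compare the observed difference with 10%. That helps, but it is not a decision rule.
- A separate analysis plan could compare a confidence bound with 0.10. However, the protocol itself fixes the success criterion, model, contrast, fallback and level, so the conflict is between stated passages rather than a detail left for later.

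**Conclusion.** The concern holds. The hypothesis in 9.1 and the rule that decides success in 4.1, 7.1 and 9.2.3 are different, and the protocol does not say which governs the claim. If 9.1 governs, the planned test does not control its error rate at 2.5% one-sided: at a true difference of 0.10 it declares A superior in 82%, 52% or 98% of trials under readings (i), (ii) and (iii). Observed differences from 0.069, 0.097 or 0.049 would count as success, where a test of the limit would need 0.169, 0.197 or 0.149. If the zero test governs, 9.1 states the wrong hypothesis and a sample size that does not belong to it.

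These sizes assume 100 completers, s_m = 0.35 and a limit of 0.10 on the same scale as A − B. The inconsistency itself needs none of these assumptions. It should be settled before the randomisation code is disclosed.

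**What to change.** Choose one of two routes and make all sections agree.

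**(a) Keep the limit.** State in 4.1, 7.1 and 9.2.3 that superiority on the primary variable is shown only if the lower limit of the two-sided 95% confidence interval for headset A minus headset B exceeds 0.10. State the scale too: 10 percentage points of X(%), if that is what was meant. If residuals are non-normal, use an interval that stays on the mean-difference scale, such as a bootstrap interval, and keep the rank ANOVA as a sensitivity analysis. The cost is a harder criterion, though power at ε = 0.25 with 100 volunteers remains 99%, 86% or above 99.9% under the three readings.

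**(b) Drop the limit.** Set δ = 0 in 9.1, restate the hypothesis and the calculated sample size (13 by formula (3)), and confine the conclusion to a difference from zero in favour of A. The cost is a weaker claim.

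Both routes change wording only. Neither needs new data or a change to the 100 volunteers.

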4.2. Description of type/design of the trial/randomization/intended purpose of the VR technology

PurePurr-001 is a randomized, prospective, sham-controlled, blinded, cross-over clinical study. The study will include healthy volunteers aged 20 to 60 years, who have applied to the study site for other medical reasons or those who read the advertisement on the Internet. After signing the Informed Consent Form for participation in the clinical study, an assessment of healthy volunteers’ eligibility with the inclusion/non-inclusion criteria will be carried out.

Study groups

Eligible volunteers will be randomized at the 1:1 ratio to one of the following study groups (1 or 2):

Group 1: the volunteers will first be tested with the VR headset A, and during the next visit – with the VR headset B.

Group 2: the volunteers will first be tested with the VR headset B, and during the next visit – with the VR headset A.

Visits

The study includes two visits:

Visit 1 (Day 1): verification of inclusion/non-inclusion criteria, randomization, and testing.

Visit 2 (Day 2): verification of exclusion criteria, testing.

The minimum interval between the two visits is 24 hours and nocturnal sleep is mandatory. The next visit should take place at the same time, taking into account the circadian rhythms. The overall

duration of the study for each volunteer is 2 days (+7 days), if necessary, Visit 2 may be postponed for a maximum period of 7 days.

Stages of each visit are described in details in Section 6.1.

Layout 1. General study layout

Group 1

Headset A, Visit 1

Stage 1	Stage 2	Stage 3	Stage 4
---------	---------	---------	---------

Headset B, Visit 2

Stage 1	Stage 2	Stage 3	Stage 4
---------	---------	---------	---------

Group 2

Headset B, Visit 1

Stage 1	Stage 2	Stage 3	Stage 4
---------	---------	---------	---------

Headset A, Visit 2

Stage 1	Stage 2	Stage 4	Stage 4
---------	---------	---------	---------

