a — limiting probability of type I error	0.05
b — limiting probability of type II error	0.05
Percentage point of the standardized normal distribution for a	1.96
Percentage point of the standardized normal distribution for b	1.64
Difference in means e	0.25
The value of clinically significant differences d	0.1
Intrasubject variability s_m	0.35
Estimated sample size	36

Thus, it is necessary to enrol 36 volunteers to this study, according to the calculations. Yet, given that a large proportion of volunteers may not meet the inclusion criteria or non-inclusion criteria, and are the non-responders, at least 80 volunteers should be enrolled to the study. Yet, since it is planned to conduct the study of the virtual reality effect separately for different groups of volunteers, it is recommended that approximately 160 volunteers are included to get 100 randomized volunteers.

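### Section 9.1 gives 36 as the study total for 95% power, but formula (3) yields 36 per sequence; the total against the 10% margin is 72 or 142, depending on what s_m means

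*Protocol*

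**What the plan says.** Section 9.1 (Justification of the sample size) sets H0: ε ≤ δ against Ha: ε > δ, where ε is the true mean difference between headset A and headset B on the primary variable, the change in HF. It frames this as "superiority under conditions of the single-group design". The inputs are δ = 0.10, ε = 0.25, s_m = 0.35, two-tailed α = 0.05 and β = 0.05, that is, a "study power of 95" per cent. Formula (3) is

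n = (z_α + z_β)² s_m² / [2(ε − δ)²].

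The text does not say whether n is a total or a number per sequence. It describes s_m as a "coefficient of variation, which is evaluated based on the results of previous studies"; the table below it lists the same quantity as "Intrasubject variability s_m".

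The table gives 36, and the conclusion drawn is: "Thus, it is necessary to enrol 36 volunteers to this study, according to the calculations". The section then says that "at least 80 volunteers should be enrolled to the study", citing ineligibility and non-responders. Finally, because groups of volunteers are to be studied separately, it recommends that "approximately 160 volunteers are included to get 100 randomized volunteers".

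Section 4.2 describes a two-sequence crossover (A then B, or B then A) with 1:1 randomisation. Section 5.3 states that volunteers who discontinue are not replaced.

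**The concern.** A single-group (paired) sample-size formula based on the SD of the difference has no 2 in the denominator. A formula with the 2 fits a balanced two-sequence crossover, but n is then the size of each sequence. Section 9.1 names the first design, uses the formula of the second, and reads the result as the study total. That halves the requirement if s_m is the SD of the A–B difference. If s_m is a within-subject SD, the stated number is about a quarter of the requirement.

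What is at stake is the power claim. The protocol states 95% power against a 10% margin, and the number it derives does not deliver that on either reading of s_m. The number actually planned, about 100, was not reached by correcting this step. It therefore has to be checked separately, and it proves sufficient on one reading only.

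**Working it through.** **Inputs (all from section 9.1):** z_α = 1.96, z_β = 1.64, ε = 0.25, δ = 0.10, so ε − δ = 0.15; s_m = 0.35. Allocation 1:1 to two sequences (section 4.2).

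**1. Reproducing the printed figure.** (1.96 + 1.64)² = 12.96 and 0.35² = 0.1225, so

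12.96 × 0.1225 / (2 × 0.15²) = 1.5876 / 0.045 = 35.28, rounded up to 36.

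The arithmetic is correct.

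**2. What n is.** With n volunteers in each sequence, N = 2n in total, and SD_d the SD of the within-volunteer A–B difference, the variance of the estimated headset effect is SD_d²/N = SD_d²/(2n). Solving for the number that gives the required power:

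- total: N = (z_α + z_β)² SD_d² / (ε − δ)²
- per sequence: n = (z_α + z_β)² SD_d² / [2(ε − δ)²]

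The second line is formula (3) with s_m = SD_d. The first is the paired, single-group formula.

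**3. Totals on the two readings of s_m.**

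- s_m is the SD of the A–B difference (SD_d = 0.35): N = 1.5876 / 0.0225 = 70.56. That is 71, or 72 when balanced at 36 per sequence.
- s_m is the within-subject SD of one result (SD_d = 0.35 × √2 = 0.495, SD_d² = 0.245): N = 12.96 × 0.245 / 0.0225 = 141.12. That is 142 when balanced, 71 per sequence.

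**4. Power.** Power = Φ(D√N / SD_d − 1.96), with D = 0.15 against the margin and D = 0.25 against zero.

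| Total completing | Null | SD_d = 0.35 | SD_d = 0.495 |
|---|---|---|---|
| 36 | margin 0.10 | 73.0% | 44.4% |
| 72 | margin 0.10 | 95.3% | 73.0% |
| 90 | margin 0.10 | 98.2% | 82.0% |
| 100 | margin 0.10 | 99.0% | 85.8% |
| 142 | margin 0.10 | 99.9% | 95.1% |
| 36 | zero | 99.0% | 85.8% |
| 100 | zero | >99.9% | 99.9% |

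Worked example for 36 and SD_d = 0.35: 0.15 × 6 / 0.35 − 1.96 = 0.611, and Φ(0.611) = 0.730. The row for 90 assumes 10% drop-out, for illustration only. Using the t distribution with N − 2 degrees of freedom changes little: against the margin, 36 gives 70.5% / 42.3% and 100 gives 98.9% / 85.1%.

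**5. Enrolment.** The protocol's own ratio is 160 / 100 = 1.6 enrolled per volunteer randomised. At that ratio 80 enrolled yield 80 / 1.6 = 50 randomised, below both totals. The totals would need 72 × 1.6 = 115.2, hence 116, or 142 × 1.6 = 227.2, hence 228. The planned 160 covers the first but not the second.

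**The case against.** - **About 100, not 36, are to be randomised.** This stands and limits the damage: power against the margin is then 99% or 86%. But 9.1 justifies 100 by the separate study of groups of volunteers, not as a correction, and on the second reading 95% is not met.
- **The analysis in section 9.2.3 is a contrast of A with B with no margin mentioned, and section 7.1 asks only for a significant difference.** Against zero, 100 volunteers give over 99% power on the first reading and about 99.9% on the second. This also stands. The shortfall therefore concerns the margin hypothesis in equation (1). That is, however, the hypothesis on which 9.1 rests its number and its 95%.
- **72 and 142 are not the only possibilities.** The two labels do not map one-to-one onto the two readings, and together could mean an intrasubject coefficient of variation. If 0.35 described a single HF value rather than a change (an assumption, with independent errors), SD_d would be 0.70 and N about 12.96 × 0.49 / 0.0225 = 282. In the other direction, 36 would be a correct total if SD_d were 0.35 / √2 = 0.247. The protocol states neither. This reinforces the need for one definition tied to the primary variable; it does not rescue 36.
- **The figure of 80 is superseded by 160 in the next sentence.** True, and the protocol does not derive 80 from the 160-to-100 ratio. The point about 80 is secondary.

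**Conclusion.** The concern holds. The calculation of 36 is right, but its use as the study total is wrong. For 95% power against the stated 10% margin the total is 72 if 0.35 is the SD of the within-volunteer A–B difference, and 142 if it is a within-subject SD, the reading closer to the table's label. As a total, 36 has 73% or 44% power.

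The planned 100 randomised volunteers give about 99% or 86% if all complete, somewhat less with drop-outs. So 95% is secured on the first reading only. These figures take the protocol's ε, δ and z values as given, use a normal approximation and assume balanced sequences. They apply to the test against the margin; against a zero difference the planned size is ample on both readings. The fault lies in the stated requirement and power, and does not by itself force a change in recruitment.

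**What to change.** Revise section 9.1 as follows.

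1. Define s_m once, for the primary variable, and use the same definition in text and table: either the SD of the within-volunteer A–B difference, or the within-subject SD, in which case enter 0.35 × √2 in formula (3). Only the protocol's authors can say which the source value is.
2. State that n in formula (3) is the number per sequence.
3. Replace 36 as the study requirement with the matching total: 36 per sequence and 72 in all, or 71 per sequence and 142 in all.
4. Replace the single-group description with a two-sequence crossover.
5. Replace the unqualified 95% with the power for about 100 randomised volunteers against the 10% margin: about 99% or about 86% if all complete, with a note that drop-outs are not replaced and lower it slightly. If power against zero is also quoted, say so.
6. Rework the minimum of 80 from the corrected total.

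The cost is wording and one table, with no new data or procedures. If s_m is a within-subject SD, the stated power falls from 95% to about 86%; keeping 95% against the margin would need 142 randomised volunteers. Otherwise enrolment can stay as planned.
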